- d Where the visit interval exceeds 4 weeks, interim shipments of IMP to patients home may be performed using direct to patient (DTP) shipping (according to local regulations and logistics), in order to provide the patient with only 4 weeks IMP at a time in order to minimize compliance errors.
- e Patient Reported Outcomes include EQ-5D-3L, FACIT-Fatigue, SF-36v2, HAQ-DI (including Pain VAS and Pt-VAS).
- f Bone mineral density assessment must be performed during baseline if not already available within 12 weeks prior to screening visit. A ±2 week time window is allowed at baseline visit and -2 week time window is allowed at EOT visit.
- g Posterior-Anterior chest X-ray must be performed during screening if not already available within 12 weeks prior to screening visit.
A standard PA chest X-ray (lateral view is also recommended but not required) is required during the screening period if no chest imaging (X-ray, Computed Tomography [CT], MRI) is available within the previous 12 weeks of V1 that clearly documents the exclusion of TB (or >12 weeks, if appropriate according to local guidelines and requirements for screening of active TB). In countries for which a specific approval procedure for the X-ray is required by a different committee than the local ethics committee/Institutional review board (EC/IRB), a chest MRI between V1 and V2 can be performed.
- h Hematology (blood to be drawn before drug administration): Hemoglobin, hematocrit, red blood cell (RBC) count and morphology (if RBC count is abnormal), white blood cell (WBC) differential, platelet count, absolute neutrophil count (ANC).
- i Chemistry (blood to be drawn before drug administration): Sodium, potassium, chloride, bicarbonate, blood urea nitrogen (BUN), creatinine and creatinine clearance, calcium, phosphate, total protein, albumin, alanine aminotransferase (ALT) (SGPT), aspartate aminotransferase (AST) (SGOT), alkaline phosphatase (ALP), total bilirubin, conjugated bilirubin, unconjugated bilirubin, lactate dehydrogenase (LDH), uric acid.
- j Blood to be drawn before drug administration.
- k Lipids: Triglycerides (TG), total cholesterol, high density lipoprotein (HDL) cholesterol, low density lipoprotein (LDL) cholesterol.

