9.2.1.4 Glucocorticoid toxicity index and components

Glucocorticoid toxicity index (GTI) is a composite scale designed to assess glucocorticoid related morbidity and potential steroid-sparing effect of treatment alternatives. The Composite GTI and Specific List constitute the overall GTI. The composite GTI consists of nine domains and 31 items that assess the potential side effects of glucocorticoid, and include evaluation of body mass index (BMI), glucose tolerance, blood pressure, lipids, bone density, steroid myopathy, skin toxicity, neuropsychiatric toxicity and infection. These are the potential CS toxicities that are likely to occur during the course of a CS treatment and may vary depending on the extent of CS exposure, and that are weighted and scored (see [Appendix C](#)).

The domains of the Composite GTI will be assessed at V2 (baseline), V6 (Week 12), V9 (Week 24), V11 (Week 40) and V12 (Week 52) (except bone density which will be assessed at baseline and Week 52 only).

- Bone mineral density assessment will be performed at V2 (baseline) and V12 (Week 52) using Dual-Energy X-ray Absorptiometry (DXA) scan, The scan can be performed within ± 2 weeks of baseline visit and -2 weeks of EOT visit, needs to include the lumbosacral and femoral neck regions. However, the baseline visit DXA scan is not required if there is one available within 12 weeks of baseline that includes the assessment of the lumbosacral and femoral neck regions. In order to minimize variability, the same machine should be used each time to obtain the scan and the machine should be well calibrated according to the recommendations of the machine's manual.

GC toxicity or the changes in GC toxicity (comparison with baseline data) for domains will be scored (score range from -36 to 439) based on the information from clinical laboratory assessments, vital sign assessments, concomitant medications and clinical assessments. The composite GTI can be reported as both a total score and domain-specific scores, in order to account for scenarios when improvements in certain domains compensate for worsening in others.

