10.2.2 Double blind period (52 weeks)

10.2.2.1 Visit 2/Baseline visit (Day 1, Week 0)

- Review of concomitant medication.
- Confirm eligibility by review of Inclusion/Exclusion Criteria.
If the patient meets all the inclusion criteria and does not meet any exclusion criteria, please conduct the following procedures in the recommended order, if possible:
- Call IRT to randomize the patient and obtain the initial treatment kit assignments.
- If the patient has been selected to complete the immunophenotyping blood sampling, the system will provide this information during the call.
- Administer PRO questionnaires (EQ-5D, FACIT-Fatigue, SF-36v2, HAQ-DI) and VAS.

Note: PRO questionnaires should be completed prior to any significant interaction with the study team and prior to any physical examination or sampling.

- Measure vital signs (including systolic and diastolic BP [mmHg], and HR [beats per minute], body temperature [°C]).
- Body weight (kg).
- GCA clinical assessments (including disease flare).
- Complete physician global assessment (MD-VAS).
- Inquire about AEs/SAEs.
- Tuberculosis assessment.
- Targeted physical examination (including head, eyes, ears, neck and throat, skin, respiratory, cardiovascular, neurologic, lymphatic examinations and abdominal examination).
- GTI Assessment.
- Bone density assessment by DXA (dual-energy x-ray absorptiometry) (± 2 week time window is allowed at baseline visit).

Note: Bone density assessment is not required if already available within 12 weeks prior to screening visit.

- Perform blood sampling (prior to administration of IMP) for the following tests:
 - Hematology and chemistry.
 - ANA.
 - CRP and ESR.
 - Serum sarilumab and ADA.
 - Biomarkers IL-6, sIL-6R.

- Serum and plasma sampling for circulating protein (for consented patients only).
- Sample for DNA and RNA for those patients who have consented to pharmacogenetics.
- Sample for circulating immune cell phenotyping for patients identified to perform this test.
- Perform urine pregnancy test (for WOCBP).
- Dispense patient diary to record injections performed at home (date, time, injection location, and local reaction or any medical events pertaining to the injection).

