2.1 ANALYSIS ENDPOINTS

2.1.1 Demographic and baseline characteristics

The baseline value is defined as the last available value prior to the first dose of study medication, SC IMP.

All baseline safety and efficacy parameters (apart from those listed below) are presented along with the on-treatment summary statistics in the efficacy and safety sections ([Section 2.4.4](#) and [Section 2.4.5](#)).

Demographic characteristics

The following demographic characteristics will be summarized separately by treatment and overall:

- Sex (Male, Female)
- Race (Caucasian/White, Black, Asian/Oriental, Other)
- Ethnicity (Hispanic, Not Hispanic)
- Region (Region 1 [Western countries], Region 2 [South America], and Region 3 [Rest of the World]); definitions of the regions are provided in [Section 2.5.7](#)
- Age (years)
- Age group (≥ 50 and < 65 , ≥ 65 and < 75 , ≥ 75 and < 85 , ≥ 85 years)
- Weight (kg)
- Weight group (< 60 , ≥ 60 and < 100 , ≥ 100 kg)
- Body mass index (BMI, kg/m^2)
- BMI group (< 25 , ≥ 25 and < 30 , ≥ 30 kg/m^2)
- Smoking status (never, former, current)
- Alcohol habits (never, occasional, monthly, weekly, daily)

Medical or surgical history

Medical or surgical history includes all the relevant findings within the lifetime of the patient.

This information will be coded to a “Lower Level Term (LLT)”, “Preferred Term (PT)”, “High Level Term (HLT)”, “High Level Group Term (HLGT)”, and associated primary “System Organ Class (SOC)” using the version of Medical Dictionary for Regulatory Activities (MedDRA) currently in effect at Sanofi at the time of database lock.

Disease characteristics at baseline

The following baseline disease characteristics as well as the other baseline characteristics will be summarized separately by treatment group:

- Unequivocal cranial symptoms of GCA (Yes, No)
- Unequivocal symptoms of PMR (Yes, No)
- Other features judged by the investigator to be consistent with GCA or PMR flares (Yes, No)
- Diagnostic temporal artery biopsy (Yes, No)
- Diagnostic imaging performed (Yes, No) and imaging methodology (Angiography, CTA, MRA, PET-CT, Ultrasound)
- Duration of GCA (from diagnosis date to baseline)
- GCA Disease onset (new onset, refractory)
- Prior GCA flares (≤ 6 months, 6 to 12 months or >12 months prior to screening)
- Prednisone dose at baseline
- Prednisone dose group at baseline (≤ 30 mg/day, >30 mg/day)
- Highest dose and duration of corticosteroid taper taken for GCA within 24 weeks prior to screening

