Clinical remission is defined as resolution of signs and symptoms and normalization of CRP (<10 mg/L). Intermittent missing CRP at visit will be imputed using last value carried forward (LOCF) approach. If missing signs and symptoms, then clinical remission is not achieved.

Glucocorticoid toxicity index (GTI) scores and components

The GTI is intended to capture glucocorticoid (GC)-related morbidity and GC-sparing ability of other therapies (2).

The GTI is composed of two components, the Composite GTI and the Specific List (Table 4). The Composite GTI consists of nine domains (body mass index (BMI), glucose tolerance, blood pressure, Hyperlipidemia, Bone Health (BMD), steroid myopathy, Skin steroid-related Toxicity, Neuropsychiatric - steroid related symptoms and infection) on common steroid-related adverse events anticipated to occur in $\geq 5\%$ of patients treated in a clinical trial involving glucocorticoids. The Specific List consists of 23 items (11 domains) that are mainly less common but serious adverse effects, serving as a complementary tool to the Composite GTI to ensure that all important elements of glucocorticoid toxicity were captured.

The domains of the Composite GTI and the specific list of the GTI will be assessed at baseline, Week 12, Week 24, Week 40 and Week 52, except for bone density (BMD) which will be assessed at Baseline and Week 52 only.

Please note, due to early termination of the study, most patients will not have BMD assessed at Week 52. In addition, for patients who withdraw from the study prior to Week 24, the BMD will not be measured at the EOT visit as no substantial changes are expected within 6 months of treatment. As a result, missing BMD score will be imputed as 'no change'. The BMD measured at the end of treatment (EOT) visit will be included in the definition of cumulative GTI scores (i.e., CWS and AIS as defined below) at Week 52 regardless when the EOT visit is occurred. The BMD domain score will be set to 'no change' in the calculation of the cumulative GTI scores at Week 24.

Scoring of the Glucocorticoid Toxicity Index (GTI)

Domain-specific score for each patient at a visit is defined as the weight assigned based on the change in severity level as described for each domain in Table 4.

Composite GTI score for each patient at a visit is the sum of 9 domain-specific scores at each visit.

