- d Where the visit interval exceeds 4 weeks, interim shipments of IMP to patients home may be performed using direct to patient (DTP) shipping (according to local regulations and logistics), in order to provide the patient with only 4 weeks IMP at a time in order to minimize compliance errors.
- e Patient Reported Outcomes include EQ-5D-3L, FACIT-Fatigue, SF-36v2, HAQ-DI (including Pain VAS and Pt-VAS).
- f Bone mineral density assessment must be performed during baseline if not already available within 12 weeks prior to screening visit. A ±2 week time window is allowed at baseline visit and -2 week time window is allowed at EOT visit.
- g Posterior-Anterior chest X-ray must be performed during screening if not already available within 12 weeks prior to screening visit.
A standard PA chest X-ray (lateral view is also recommended but not required) is required during the screening period if no chest imaging (X-ray, Computed Tomography [CT], MRI) is available within the previous 12 weeks of V1 that clearly documents the exclusion of TB (or >12 weeks, if appropriate according to local guidelines and requirements for screening of active TB). In countries for which a specific approval procedure for the X-ray is required by a different committee than the local ethics committee/Institutional review board (EC/IRB), a chest MRI between V1 and V2 can be performed.
- h Hematology (blood to be drawn before drug administration): Hemoglobin, hematocrit, red blood cell (RBC) count and morphology (if RBC count is abnormal), white blood cell (WBC) differential, platelet count, absolute neutrophil count (ANC).
- i Chemistry(blood to be drawn before drug administration): Sodium, potassium, chloride, bicarbonate, blood urea nitrogen (BUN), creatinine and creatinine clearance, calcium, phosphate, total protein, albumin, alanine aminotransferase (ALT) (SGPT), aspartate aminotransferase (AST) (SGOT), alkaline phosphatase (ALP), total bilirubin, conjugated bilirubin, unconjugated bilirubin, lactate dehydrogenase (LDH), uric acid.
- j Blood to be drawn before drug administration.
- k Lipids: Triglycerides (TG), total cholesterol, high density lipoprotein (HDL) cholesterol, low density lipoprotein (LDL) cholesterol.

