Appendix H Visit windows based on day ranges

Visit windows based on days relative to the first IMP dose will be used to map (see [Table 9](#)).

Table 9 - Day range for each scheduled visit in the DB period for efficacy, lab, vital sign, PK and ADA summaries

Visit Label	Target Day	Schedule A ^a	Schedule B ^b	Schedule C ^c	Schedule D ^d	Schedule E ^e	Schedule F ^f	Schedule G ^g	Schedule H ^h	Schedule I ⁱ	Schedule J ^j
Double-Blind Period											
Baseline	1	≤1	≤ 1	≤ 1	≤ 1	≤ 1		≤ 1	≤ 1	≤ 1	≤ 1
Week 2	15	>1'- 21							>1'-21	>1'-49	
Week 4	29	22-42				>1'-56	>1'-56	>1'-42	22 - 56		>1'-98
Week 8	57	43-70						43 - 70			
Week 12	85	71-98	>1'-126	>1'-126		57 - 126	57 - 126	71 - 98	57 - 98	50 - 126	
Week 16	113	99-126						99 - 126	99 - 140		
Week 20	141	127-154						127 - 154			
Week 24	169	155-196	127 - 224	127 - 266		127 - 224	127 - 224	155 - 196	141 - 266	127 - 266	≥ 99
Week 32	225	197-252						197 - 252			
Week 40	281	253-322	225 - 322			225 - 322	225 - 322	253 - 322			
Week 52	365	≥323	≥ 323	≥ 267	>1'	≥ 323	≥ 323	≥ 323	≥ 267	≥ 267	

a Includes temperature, heart rate, blood pressure, GCA clinical assessments (including disease flare), CRP, ESR

b Includes weight, glucocorticoid toxicity index (excluding bone density assessment)

c Includes physician global assessments (MD-VAS), patient reported outcomes and antibodies to sarilumab/ADA

d Includes bone density assessment, ANA

e Includes hematology: hemoglobin, hematocrit, red blood cell (RBC) count and morphology (if RBC count is abnormal), white blood cell (WBC) differential, platelet count, absolute neutrophil count (ANC) and chemistry: sodium, potassium, calcium, chloride, bicarbonate, total protein, creatinine and clearance, blood urea nitrogen (BUN), uric acid, lactate dehydrogenase (LDH), phosphate, albumin, ALT (SGPT), AST (SGOT), alkaline phosphatase (ALP), total bilirubin, conjugated bilirubin, and unconjugated bilirubin

f Includes HbA1c, fasting glucose, fasting lipids: triglycerides (TG), total cholesterol, HDL, LDL

g Includes urine pregnancy test

h Includes serum sarilumab

i Includes biomarkers-IL-6 and sIL-6R

j Includes immune cell phenotyping (whole blood)

* Includes value measured on day 1 but after the first IMP dose

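### A baseline bone-density scan done after the first dose, as the protocol permits, is filed by the SAP as Week 52, leaving a later end-of-treatment scan with no baseline

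*SAP*

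**What the plan says.** **When the scan may be done.** Protocol 1.2, flow-chart footnote f: "A ±2 week time window is allowed at baseline visit and -2 week time window is allowed at EOT visit". SAP Appendix A repeats this footnote. Protocol 9.2.1.4 gives the same limits ("weeks of baseline visit and -2 weeks of EOT visit"), and the Visit 2 procedures in Protocol 10.2.2.1 carry the same two weeks either side. An existing scan can stand in: under 9.2.1.4, "the baseline visit DXA scan is not required if there is one available within 12 weeks of baseline". The flow chart and 10.2.2.1 count the 12 weeks back from screening instead.

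**What counts as baseline.** SAP 2.1.1: "The baseline value is defined as the last available value prior to the first dose of study medication, SC IMP".

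**How scans are mapped to visits.** SAP 2.5.4 maps efficacy measurements by day relative to the first IMP dose. If several scheduled measurements fall in one window, the one nearest the target day is used. An empty window means the visit is missing. In Table 9, Schedule D ("d Includes bone density assessment, ANA") has two windows: baseline at Day 1 or earlier, and Week 52 (target Day 365) for anything later. A table note puts a Day 1 value taken after the first dose in the later window.

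**What happens to a missing score.** SAP 2.1.3.2 says that a "missing BMD score will be imputed as" no change. It also counts the EOT scan toward Week 52 whenever the EOT visit falls, and fixes the BMD domain at no change for every patient at Week 24.

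**The concern.** The collection rule and the analysis rule disagree about the same scan. A site that does the baseline DXA in the two weeks after Day 1 has followed the protocol, yet the SAP does not accept the result as a baseline and gives it a Week 52 label. BMD is one of the nine domains of the composite GTI. It feeds the Week 52 cumulative worsening score (CWS) and aggregate improvement score (AIS), which SAP 2.4.4.2 compares between the combined groups by ANCOVA with a 95% CI and p-value, and by odds ratios around a cut at zero. A usable pair of scans could be discarded and a real change entered as zero. Early termination already thins out the follow-up bone data, so this loss is avoidable.

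A likely cause is that BMD shares Schedule D with ANA. ANA is drawn before IMP at Visit 2 and has no two-week allowance, so the cut at Day 1 suits ANA but not DXA.

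**Working it through.** There is no stated figure to reproduce. The check is to follow one compliant patient through the rules.

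**Inputs**
- Latest permitted baseline scan: Day 1 + 14 = Day 15 (Protocol 1.2, 9.2.1.4, 10.2.2.1; SAP Appendix A).
- Windows: baseline ≤ Day 1 and pre-dose; Week 52 is everything after (SAP Table 9).
- Selection: nearest to Day 365; empty window is missing (SAP 2.5.4).
- BMD weights: loss of more than 3% scores +29, gain of more than 3% scores −29, otherwise 0 (SAP Table 4).
- Missing BMD score: no change, that is, 0 (SAP 2.1.3.2).
- Week 52 Analysis set: 36 of 83 patients (SAP 2.3.1).

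**Overlap.** The protocol permits scans up to Day 15. Table 9 files everything after the first dose as Week 52. Every scan from later on Day 1 through Day 15 is therefore both a compliant baseline scan and a Week 52 value.

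**Applying the rules as written.** Take one baseline scan, one EOT scan on Day 200, 351 or 365, and a true change of −5% or +5%. Each row below covers 3 scan days × 3 EOT days × 2 changes = 18 cases.

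| Baseline scan on | Baseline value | Week 52 value | BMD score, SAP as written | BMD score, baseline window to Day 15 |
|---|---|---|---|---|
| Day −14, −1, or 1 pre-dose | present | EOT scan | +29 or −29, correct in 18 of 18 | same |
| Day 2, 8 or 15 | missing | EOT scan (nearer Day 365) | 0 in 18 of 18 | +29 or −29, correct in 18 of 18 |

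**Effect per patient**
- AIS: a loss should add 29 and a gain should subtract 29. Both become 0, an error of 29 points.
- CWS: only positive scores count, so a loss is understated by 29 points and a gain is unaffected.
- A change within 3% scores 0 under either rule.

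**Effect on a group mean, as illustration.** The split of the 36 patients is not given. If it follows the 2:1:1:2 ratio, each combined group has 36 × 3/6 = 18 patients. One mis-scored patient then moves that group's unadjusted mean by 29/18 = 1.6 points.

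**No EOT scan.** The early scan is the only value in the Week 52 window and is reported there. No change could have been computed under any window, so no change score is lost.

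**The case against.** The strongest reply is that the plan does not clearly prescribe the wrong score. The no-change sentence in SAP 2.1.3.2 follows a discussion of missing follow-up scans and does not name a missing baseline. The same section ties the Week 52 BMD value to the EOT visit, so a programmer might reasonably decline to treat a baseline-visit scan as an EOT value, or might use the visit label on the CRF. Part of this stands: scoring a missing baseline as no change is an inference. But a change without a baseline is a missing score, and no other rule covers it; the carry-forward rule in SAP 2.5.2 is for laboratory measurements. SAP 2.5.4 maps by day, with no exception for BMD. Reading the Week 52 value as the EOT scan would avoid the mislabelling but would not restore the baseline.

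The second reply is that little depends on this. BMD enters the Week 52 sums once, with at most 29 points, against a maximum of 439 per visit (36 + 44 + 44 + 30 + 29 + 63 + 26 + 74 + 93), in scores that add four visits. Efficacy analyses are descriptive and p-values nominal (SAP 2.4.4, 2.4.4.3). That stands and limits the weight of the point.

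Several stronger readings are tempting but unsupported:
- A reader might infer that every late scan costs the patient a baseline. A patient with an earlier pre-dose scan keeps one.
- A reader might infer that most patients have no EOT scan. SAP 2.1.3.2 says most will lack a scan at Week 52; it rules out the EOT scan only for withdrawals before Week 24.
- A reader might put a number on it: 10% to 30% of 36 is 3.6 to 10.8 patients. That share is an assumption with no support in the documents. It would also count late scans rather than wrong scores, which further need no earlier pre-dose scan, an EOT scan and a change above 3%.

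**Conclusion.** The conflict is in the text and the rule is wrong as written, with a narrow effect. A score is lost only when the sole baseline scan is post-dose (later on Day 1 through Day 15), an EOT scan exists, and the true change exceeds 3%. Each such patient loses 29 points from Week 52 AIS (gain or loss) or from CWS (loss only). This rests on reading the no-change rule as covering a missing baseline. Where there is no EOT scan, the fault is only one of labelling.

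The reach is the Week 52 CWS and AIS in the 36-patient set, plus the BMD summaries. Week 24 is unaffected. The number of affected patients is unknown, so the documents do not support a claim that the treatment comparison is materially distorted. The point is worth correcting because the repair is simple and uses data already collected.

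**What to change.** Before database lock:

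1. In SAP Table 9, separate bone density from ANA. Leave ANA as it is.
2. Define BMD baseline as the last pre-dose scan or, only if none exists, the first post-dose scan up to Day 15.
3. Start the BMD Week 52/EOT window after Day 15, so that a baseline scan cannot fall into it. The rule that an EOT scan counts whenever EOT occurs can stay.
4. Add the matching BMD exception to the baseline definition in SAP 2.1.1.

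A simpler rule, taking the scan closest to Day 1, is not advisable: it could replace a valid pre-dose scan with an on-treatment one. The pre-dose-first order keeps the general baseline principle and departs from it only where the protocol's own allowance makes that necessary.

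The cost is a few lines of SAP text and one change to the derivation. No new data are needed. Using a scan from the first two weeks as baseline is in line with SAP 2.1.3.2, which expects no substantial BMD change within six months. Reporting how many patients relied on a post-dose baseline scan would show the actual size of the issue.
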